Given that oxytocin is involved in the regulation of a variety of dimensions of social cognition and behavior, including emotion recognition and social information processing, there are direct implications regarding its role in the development of such deficits among individuals BDD in particular. Individuals with BDD display deficits in social cognition, as they are convinced that their appearance is flawed, and that people may be staring and laughing at their physical flaws. Experiments have shown that BDD is associated with selective attentional biases to imagined flaws in one's own face and to corresponding regions in unfamiliar others' faces (e.g., Grochowski, Kleim, & Heinrichs, 2012). Moreover, research has shown that individuals with BDD incorrectly interpret faces showing neutral emotional expressions as contemptuous and angry (Buhlmann, Etcoff, & Wilhelm, 2006). Despite these obvious problems with regard to social cognition, no studies have yet examined the effect of oxytocin in BDD. The current study therefore aims to investigate the effect of oxytocin administration on modifying core social cognitive impairments associated with BDD. This study has major public health significance, given the prevalence of OC spectrum disorders and the need to investigate more parsimonious treatments.

II. Specific Aims

Primary Aim 1: To examine differential effects of oxytocin on social cognitive deficits during an emotion recognition task and trust game by diagnosis.

Hypothesis 1a: Individuals with BDD will exhibit poor performance on the emotion recognition task and trust game, compared to healthy controls.

Hypothesis 1b: The effects of oxytocin vs. placebo on the emotion recognition task and trust game will be greater for individuals with BDD than for healthy controls.

Secondary Aim 2: To examine the effect of oxytocin on cognitive biases (attentional and interpretive biases) associated with BDD.

Hypothesis 2a: Individuals with BDD (compared to healthy controls) will exhibit the following cognitive biases: attentional bias (difficulty disengaging from threat cues, as measured by a spatial cueing paradigm), and negative interpretive bias (as measured by an interpretation questionnaire).

Hypothesis 2b: For individuals with BDD (compared to healthy controls), oxytocin will attenuate these biases compared to placebo.

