Prior to analysis, all major variables will be screened for inconsistent or abnormal values, and continuous measures assessed for skewness and outliers. Variable distributions will be examined and transformations made when distributions are skewed or otherwise violate analytic assumptions. Linear regression models will be used, and in all models, the effect of diagnosis will be based not on the global (type III) effect, but on the specific pair-wise comparison of interest: BDD vs. Healthy Controls. Analyses will be conducted using SAS v9.4 (SAS Institute, Cary, NC), and all models will employ a two-sided alpha=0.05 to determine significance.

Aim 1 Analyses:

The primary outcomes will be the Emotion Recognition Task total score and the Trust Game "back transfer" amount. Two sets of outcome scores will be obtained for each subject - one during placebo and the other during oxytocin administration. To test Hypothesis 1a, we will regress placebo outcome scores against diagnosis. To test Hypothesis 1b, we will regress oxytocin outcome scores against diagnosis, and will control for the placebo outcome score. If we find significant differences in oxytocin Emotion Recognition Task total score by diagnosis, we will further examine the 3 Emotion Recognition Task valence categories (positive, negative, neutral) as exploratory outcomes.

Aim 2 Analyses:

Secondary outcomes include the Posner Task difference score for disengagement response latencies between disgust vs. neutral faces, and the Interpretation Questionnaire total score. Mirroring the analyses for the primary aim, we will test Hypothesis 2a by regressing the placebo secondary outcome scores against diagnosis, and will test Hypothesis 2b by regressing the oxytocin secondary outcome scores against diagnosis, controlling for the placebo secondary outcome scores.

Exploratory Analyses:

Exploratory moderators include the BDD-YBOCS total score, YBOCS total score, LSAS total score, BFNE total score, ECR Anxiety subscale mean, ECR Avoidance subscale mean, and IPSM total score. To test the moderation effects, we will enter each moderator (one at a time) into each of the aforementioned linear regression models along with a covariate representing the interaction between the moderator and diagnosis (the term of interest). We will examine moderation of each pair-wise comparison separately.

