For all analyses, we will include concomitant medication use as a covariate, in order to control for the effect of concomitant medications on study results. We will also compare participants who are taking psychotropic medications from participants who are not, on

demographic and clinical variables, to ensure there are no systematic differences between these groups.

Power and Sample Size:

Given the novelty of our approach, no background data on the effects of oxytocin in BDD exist to inform the power calculation. Therefore, the proposed sample size of 40 participants (20 per group) was chosen based on feasibility. With 20 participants per group and a two-sided alpha=0.05, for our primary pair-wise comparison (BDD vs. healthy controls) of the mean within-subject difference (oxytocin vs. placebo) in Emotion Recognition Task total score and Trust Game "back transfer" amount, we will have 81% power to detect a moderate effect size of $f=0.23$.

VII. Risks and Discomforts

Oxytocin-Related Risks and Side Effects:

Between 1990 and 2010, there have been 38 controlled studies involving intranasal delivery of oxytocin (MacDonald et al., 2011). A total of 1,529 participants have received intranasal oxytocin or placebo, and nine studies have included participants (N=182) who had a developmental, medical, or mental health disorder. The dosage of oxytocin has typically been a single dose ranging from 20 international units (IU) to 40 IU. Out of the 1,529 participants who have received intranasal oxytocin or placebo, 279 (18%) reported mild side-effects (MacDonald et al., 2011). The most common side-effect was a feeling of calmness, but this did not differ between those who received oxytocin or placebo. A recent review of studies using intranasal oxytocin supported the short-term use of oxytocin, demonstrating that oxytocin produced minimal side-effects, no detectable differences in side-effects between oxytocin or placebo recipients, no subjective changes in recipients, and is equally safe to use with vulnerable populations as with healthy adults (MacDonald et al., 2011). The proposed study intends to use a single 24 IU dose of intranasal oxytocin, which has been the most commonly used dose in previous trials (25 out of 38 studies).

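### The power sentence leaves f and the between-visit correlation undefined, and 81% power with 20 per group corresponds to about 0.92 SD of the oxytocin-placebo difference, which is not a moderate effect

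*Combined protocol and SAP*

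**What the plan says.** Section VI, Power and Sample Size, says that "no background data on the effects of oxytocin in BDD exist to inform the power calculation" and that "the proposed sample size of 40 participants (20 per group) was chosen based on feasibility". It then gives a power figure for the BDD-versus-control comparison "of the mean within-subject difference (oxytocin vs. placebo) in Emotion Recognition Task total score" and in the Trust Game amount: "we will have 81% power to detect a moderate effect size of $f=0.23". Nothing in the document says which f is meant. No between-visit correlation or standard deviation is given, and the effect is not translated into task points or game dollars.

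The analysis planned for Hypothesis 1b is a different one. Under Aim 1 Analyses, "we will regress oxytocin outcome scores against diagnosis, and will control for the placebo outcome score". The text just before Power and Sample Size adds: "For all analyses, we will include concomitant medication use as a covariate". At the start of section VI, "all models will employ a two-sided alpha=0.05 to determine significance".

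**The concern.** This is the plan's only statement of what the primary comparison can detect. A reader will take it to mean that a moderate diagnosis-by-drug effect would probably be found, and may then read a null Hypothesis 1b result as evidence against such an effect.

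The symbol f has several meanings. One turns 0.23 into a bit under half an SD of the difference, and another turns it into nearly a whole SD. The power differs greatly between them. On the scale the sentence names, a modest effect and 81% power do not go together at 20 per group.

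**Working it through.** **Inputs from section VI.** N = 40 (20 per group), two-sided alpha 0.05, f = 0.23, stated power 81%. The contrast is BDD minus control on the oxytocin-minus-placebo difference. The correlation ρ between a participant's two visits is not given, so every value of ρ below is an assumption.

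**1. Reproducing the 81%.** Take f as the group-by-drug interaction f in a 2×2 repeated-measures design (m = 2 visits, F test on 1 and 38 df):

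λ = N × m × f² / (1 − ρ) = 40 × 2 × 0.0529 / (1 − ρ) = 4.232 / (1 − ρ)

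| ρ (assumed) | λ | Power |
|---|---|---|
| 0 | 4.232 | 51.8% |
| 0.3 | 6.046 | 66.9% |
| 0.5 | 8.464 | 80.9% |
| 0.7 | 14.107 | 95.5% |

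Only a correlation close to 0.5 gives 81%. The figure reproduces, but it depends on an input that the plan does not state.

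**2. What f = 0.23 means on that reading.** The difference between groups in mean drug effect is 4f = 4 × 0.23 = 0.92 single-visit SD. The SD of the within-subject difference is √(2(1 − ρ)) single-visit SD, which is 1 at ρ = 0.5. The effect is therefore 0.92 SD on both scales.

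**3. The ordinary two-group f on the difference.** Here d = 2f = 0.46 SD of the difference, and λ = N f² = 40 × 0.0529 = 2.116. Power is 29.4%.

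**4. A check that does not depend on what f means.** For an unadjusted two-group comparison of differences, λ = (20/2) × d² = 10 d², with d in SD of the difference (38 df).

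- d = 0.92: λ = 8.464, power 80.9%. Exactly 81% needs d = 0.921.
- d = 0.5: λ = 2.5, power 33.8%.

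**5. Could the effect be moderate in single-visit units?** An effect of δ single-visit SD is δ / √(2(1 − ρ)) SD of the difference. For 81% power, δ = 0.5 needs ρ of about 0.853 and δ = 0.46 needs ρ of about 0.875. The plan gives no support for either value. Both still come to 0.92 SD of the difference: 0.5 / √(2 × 0.147) = 0.92 and 0.46 / √(2 × 0.125) = 0.92.

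**6. The planned model.** Suppose the covariates are exactly balanced between groups. Adjusting for the placebo score then changes the noncentrality to λ = 10 d² × 2(1 − ρ)/(1 − ρ²) = 20 d² / (1 + ρ), on 36 df with the medication term. At d = 0.5, λ is 3.85, 3.33 and 2.94, and power is 48%, 43% and 39%, at ρ = 0.3, 0.5 and 0.7. Even in this favourable case the covariates do not bring 0.5 SD near 81%.

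**The case against.** **The plan is open about its basis.** It says that no prior data exist and that the sample size rests on feasibility. No test or decision rule uses f = 0.23, and the document nowhere says that a null result would exclude a moderate effect. All of this stands. It makes the point one of reporting and interpretation, but it does not make the sentence accurate.

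**The label *moderate* belongs to f, and 0.5 SD is a yardstick the plan did not choose.** This is fair as far as it goes. Yet the sentence applies f to a difference in means, and on that scale 81% power corresponds to 0.92 SD by sample size and alpha alone.

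**The reading in step 1 is not the only match.** A paired test on all 40 participants at d = 0.46 also gives 81.0%, though that is not the group contrast described. A single-visit d of 0.46 with a correlation near 0.87 also gets there. The origin of the 81% is therefore inferred. Step 4 does not depend on it.

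**A reader might infer that the 81% is simply wrong.** The documents do not support that, because it reproduces under a standard formula with correlation 0.5.

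**A reader might also infer that planned-model power can be quoted in its place.** The figures in step 6 assume equal placebo scores in the two groups, whereas Hypothesis 1a expects that "Individuals with BDD will exhibit poor performance on the emotion recognition task and trust game, compared to healthy controls". They also assume that medication use is unrelated to diagnosis. Controls must have no current Axis I disorder, while BDD participants may take psychotropic medication, so an association is likely. If use were 60% against 5% (an assumption), power at 0.5 SD falls to about 32%, 29% and 26% at correlations 0.3, 0.5 and 0.7.

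**Nor can the plan claim higher power for effects that lower BDD scores.** Suppose BDD placebo scores are 0.5 SD lower and the drug effect is the same in both groups. The adjusted model then still rejects about 18 to 19%, 14% and 9 to 10% of the time at those correlations, nearly all in that direction. Part of that apparent power is bias from adjusting for a score that differs by group, which is a separate issue.

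**Conclusion.** The concern holds as a defect in how the detectable effect is stated. With 20 per group and two-sided alpha 0.05, an unadjusted comparison of the within-subject difference has 81% power at about 0.92 SD of that difference and 34% at 0.5 SD. These two figures rest only on the stated sample size and alpha and on the usual normal, equal-variance model. The explanation of the 81% as an interaction f at correlation 0.5 is an inference.

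The consequence is limited to how a null Hypothesis 1b result is read: it would not exclude a moderate effect. A reader might go further and infer that enrolment must change or that the planned test is invalid on this ground. The documents do not support either, since the sample was set by feasibility and no test depends on f. The point should be fixed, and the fix is small.

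**What to change.** Replace the power sentence with wording such as:

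> With 20 per group and two-sided alpha 0.05, an unadjusted comparison of the within-subject oxytocin-placebo difference has 81% power at 0.92 SD of that difference and 34% power at 0.5 SD; a non-significant result does not exclude a moderate effect.

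Alternatively, keep 81% and f = 0.23, but state that f is the repeated-measures interaction f with an assumed correlation of 0.5 (if that is what was used), give the equivalent 0.92 SD of the difference, and delete *moderate*.

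In either case, add that the Hypothesis 1b model adjusts for the placebo score and medication use. Its power therefore differs, and it depends on the between-visit correlation, on any group difference in placebo score and on any association of medication use with diagnosis. Do not put planned-model power figures in the protocol, or a claim of higher power for effects that lower BDD scores.

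The cost is a few sentences of wording and a less favourable stated figure. Enrolment and analysis stay as they are.
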